6.1 Full Analysis Set

The full analysis set includes all enrolled subjects who have received at least 1 dose of Repatha. Unless specified otherwise, the FAS will be the default analysis set in this study.

6.1.1 Primary Analysis Set

The primary analysis set is the full analysis set (FAS).

6.2 Safety Analysis Set

The safety analysis set is the full analysis set (FAS).

6.3 Per Protocol Set(s)

Not applicable.

6.4 Health-related Quality-of-Life or Health Economics Analyses Set(s)

Not applicable.

6.5 Pharmacokinetic/Pharmacodynamic Analyses Set(s)

Not applicable.

6.6 Interim Analyses Set(s)

There is no planned interim analysis for this study.

Protocol Number: 20170199

Date: 09 March 2019 Page 11 of 19

6.7 Study-specific Analysis Sets

Not applicable.

7. Planned Analyses

7.1 Interim Analysis and Early Stopping Guidelines

There is no planned interim analysis for this study.

7.2 Primary Analysis

Not applicable.

7.3 Final Analysis

The final analysis will be performed at the end of the study (defined as when the last subject enrolled has completed the safety follow-up/EOS visit).

8. Data Screening and Acceptance

8.1 General Principles

The objective of the data screening is to assess the quantity, quality, and statistical characteristics of the data relative to the requirements of the planned analyses.

8.2 Data Handling and Electronic Transfer of Data

The Amgen Global Study Operations-Data Management (GSO-DM) department will provide all data to be used in the planned analyses. This study will use the RAVE database.

All data collected in the eCRF will be extracted from RAVE. Protocol deviations will be transferred from eClinical. Details on data transfer will be provided in the Data Transfer Plan.

8.3 Handling of Missing and Incomplete Data

8.3.1 Patterns of Missing Data

Subjects may be missing specific data points for various reasons. In general, data may be missing due to a subject's early withdrawal from study, a missed visit, or non-evaluability of a data point or an endpoint at a particular point in time. In the Data Issue Identification and Resolution (DIIR) processes, queries will be made to the sites to distinguish true missing values from other unknown values (eg, due to measurement or sample processing error).

All attempts will be made to capture missing or partial data for this trial prior to the database lock.

There will be no imputation for missing data.

Protocol Number: 20170199

Date: 09 March 2019 Page 12 of 19

8.3.2 Handling of Incomplete Dates

Adverse event and concomitant medications with completely or partially missing dates will be queried. After the query is resolved, if the date is still incomplete with year only or year and month only, the start date will be imputed as described in Table below:

Table 8-1. Imputation Rules for Incomplete Dates

	Missing	Imputation	Exception
Start date (AE and concomitant medication)	Day	1	Default to Study Day 1 if an event starts the same year and month as Study Day 1
	Day/Month	1-Jan	Default to Study Day 1 if an event started the same year as Study Day 1

8.4 Detection of Bias

Major protocol deviations likely to impact the analysis and interpretation of the endpoints have the potential to bias the results of the study. Important protocol deviations likely to impact the analysis and interpretation of the efficacy endpoints will be tabulated in the Clinical Study Report (CSR).

Because of its prospective, observational nature, this study is more greatly affected by bias than interventional clinical trials. Missing or incomplete data is a potential risk for bias. Before the study begins, initiation visits will be carried out to complete site trainings for the protocol and other study specific procedures. The investigator will be given clear guidelines for CRF completion for this study to ensure that he/she makes every effort to collect complete data. In the Data Issue Identification and Resolution (DIIR) process, queries will be made to the sites minimize the missing data as described in Section 8.3.1.

8.5 Outliers

Various methods, including univariate summaries, histograms, scatterplots, box plots, and line graphs, may be used to identify outliers in key safety and efficacy variables. Extreme data points will be identified during the blinded review of the data prior to database lock. Such data points will be reviewed with clinical data management to ensure accuracy. The primary analyses will include outliers in the data. Sensitivity analyses may be undertaken if extreme outliers for a variable are observed.

Protocol Number: 20170199

Date: 09 March 2019 Page 13 of 19

8.6 Distributional Characteristics

Statistical analyses in this study are descriptive in nature. There are no distributional requirements for the planned analyses.

8.7 Validation of Statistical Analyses

Programs will be developed and maintained and output will be verified in accordance with current risk-based quality control procedures.

Tables, figures, and listings will be produced with validated standard macro programs where standard macros can produce the specified outputs.

The production environment for statistical analyses consists of Amgen-supported versions of statistical analysis software; for example, the SAS System version 9.4 or later.

9. Statistical Methods of Analysis

9.1 General Considerations

Statistical analyses in this study will be descriptive in nature. No statistical inference is planned. There will be no imputation for missing data.

Subject disposition, demographics, and baseline characteristics will be summarized.

Summary statistics for continuous variables will include the number of subjects, mean, median, standard deviation or standard error, minimum and maximum. For categorical variables, the frequency and percentage will be given.

Final analyses will be based on data collected from this study. The final analysis will be conducted when all subjects have either completed all the scheduled study visits or have early terminated from the study. At that time, the database will be cleaned, processed and locked. All endpoints will be analyzed based on this snapshot.

9.2 Subject Accountability

The number of subjects screened, enrolled, receiving IP, and completing the study will be summarized from all enrolled subjects. Study discontinuation and IP discontinuation will be tabulated separately by reasons for discontinuation from all enrolled subjects.

The number of subjects included in and excluded from the full analysis set will be summarized.

9.3 Important Protocol Deviations

Important Protocol Deviations (IPDs) categories are defined by the study team before the first subject's initial visit and updated during the IPD reviews throughout the study

Protocol Number: 20170199

Date: 09 March 2019 Page 14 of 19

prior to database lock. These definitions of IPD categories, subcategory codes, and descriptions will be used during the course of the study. Eligibility deviations are defined in the protocol.

9.4 Demographic and Baseline Characteristics

Baseline demographics, weight, cardiovascular medical history, laboratory parameters, vital signs and concomitant medication will be summarized for all enrolled subjects.

9.5 Efficacy Analyses

The percent change from baseline to week 12 for LDL-C, ApoB and Lp(a) will be summarized. In addition, descriptive statistics of actual values and change from baseline will be provided.

9.5.1 Analyses of Primary Efficacy Endpoint(s)

Not applicable.

9.5.2 Analyses of Secondary Efficacy Endpoint(s)

Descriptive statistics will be summarized for each secondary endpoint.

9.5.3 Analyses of Exploratory Efficacy Endpoint(s)

Not applicable.

9.6 Safety Analyses

9.6.1 Analyses of Primary Safety Endpoint(s)

Subject incidence of treatment-emergent adverse events will be summarized.

9.6.2 Adverse Events

The Medical Dictionary for Regulatory Activities (MedDRA) version [21.0] or later will be used to code all events categorized as adverse events and disease-related events to a system organ class and a preferred term.

The subject incidence of adverse events will be summarized for all treatment-emergent adverse events, serious adverse events, adverse events leading to withdrawal of investigational product, fatal adverse events and adverse events of interest.

Subject incidence of all treatment-emergent adverse events, serious adverse events, adverse events leading to withdrawal of investigational product, and fatal adverse events will be tabulated by system organ class and preferred term in alphabetical order.

Subject incidence of events of interest (standardized MedDRA queries and/or Amgen customized queries) will also be summarized according to their categories and preferred term. Current event of interest to be analyzed is hypersensitivity for this study.

Protocol Number: 20170199

Date: 09 March 2019 Page 15 of 19

Summaries of treatment-emergent and serious adverse events will be tabulated by system organ class and preferred term.

Subject incidence of disease-related events will be summarized for all treatment-emergent disease-related events and fatal disease-related events.

9.6.3 Laboratory Test Results

Descriptive statistics will be provided for actual values and changes from baseline in selected laboratory parameters at protocol-specified scheduled visits provided in the protocol Table 2-1. Laboratory analytes are provided in the protocol Table 12-1.

9.6.4 Vital Signs

Systolic and diastolic blood pressure and heart rate will be summarized using descriptive statistics at each scheduled visit. Summaries will also include the change from baseline at each scheduled visit.

9.6.5 Physical Measurements

Weight (in kilograms) will be summarized as baseline characteristics. Descriptive statistics will be provided.

9.6.6 Electrocardiogram

Not applicable.

9.6.7 Antibody Formation

Not applicable.

9.6.8 Exposure to Investigational Product

Descriptive statistics will be produced to describe the patient-month exposure to investigational product and patient-month duration of study participation.

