7.1 Treatment Procedures

7.1.1 Investigational Products

Table 7-1. Study Treatments

Study Treatment Name	Amgen Investigational Product: ^a Repatha
Dosage Formulation	Repatha will be presented as a sterile, preservative-free solution in a single-use, disposable, handheld mechanical (spring-based) prefilled Al/pen for fixed dose, SC injection. The prefilled Al/pen contains a 1-mL deliverable volume of 140 mg/mL evolocumab.
Unit Dose Strength(s)/ Dosage Level(s) and Dosage Frequency	140 mg/mL 420 mg QM (subjects on apheresis: 420 mg Q2W)
Route of Administration	SC
Accountability	The amount dispensed, amount returned, date dispensed, date returned, package lot number of Repatha is to be recorded on each subject's eCRF(s).
Dosing Instructions	Subjects have the option of self-administration, defined as SC administration of IP by the subject, designee, or a qualified health care professional in a non-investigator site setting (eg, at home). If IP is administered on site, it must be performed after all scheduled assessments. After IP administration at the first dosing visit, subjects will remain at site for observation for at least 30 minutes before being discharged.
Device	Al/pen

Al/Pen = autoinjector/pen; eCRF = electronic case report form; IP = investigational product; QM = once monthly; Q2W = every 2 weeks; SC = subcutaneous

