10.4.2.3.3 Exposure to Investigational Product

The number of days on investigational product and the total dose of investigational product will be summarized using descriptive statistics.

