3.1 Study Design

This open-label, multicenter, non-comparative phase 4 study of Repatha is part of Amgen's post marketing requirement to the Indian Regulatory Authority. The study population consists of approximately 30 Indian subjects with HoFH and for whom Repatha is indicated in accordance with the approved prescribing information in India.

The assignment of subjects to protocol treatment will be decided by the investigator according to inclusion/exclusion criteria and laboratory assessments at screening (including fasting lipids). Subjects who are enrolled will be instructed to continue to follow a diet limiting saturated fat to less than 7% of total daily calories and will be required to maintain their current lipid-lowering drug therapy throughout the duration of the trial. Subjects will receive Repatha 420 mg once monthly (QM) subcutaneous (SC) and study visits will occur approximately every 4 weeks. For subjects on

Protocol Number: 20170199

Date: 09 March 2019 Page 7 of 19

apheresis, they may receive Repatha 420 mg SC every 2 weeks to correspond with their apheresis schedule. Final administration of Repatha will occur at week 8. The end of study (EOS) visit and the last estimation of lipids will occur at week 12 for all subjects.

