5.3 Other Related Definitions

Analytical Study Week Assignments

Analytical windows will be used to assign parameters to study weeks. The algorithm is provided in Appendix A. .

Investigational Product (IP)

IP is Repatha 420 mg QM SC.

IP Exposure Period in Months

IP Exposure Period = [min (Last IP Dose Date + 28 days, EOS Date) – First IP Dose Date + 1] / 365.25 * 12

Treatment Emergent Adverse Events

Events are categorized as Adverse Events (AEs) starting on or after first dose of investigational product as determined by the flag indicating if the value of the Events eCRF question "Did event start before first dose of investigational product?" is No or

Protocol Number: 20170199

Date: 09 March 2019 Page 10 of 19

missing and up to including 30 days after the end of investigational product or the End of Study date, whichever is earlier.

Treatment Emergent Disease-Related Events

Treatment emergent disease-related events are events categorized as Disease-related Events (DREs) starting on or after first dose of investigational product as determined by the flag indicating if the value of the Events eCRF question "Did event start before first dose of investigational product?" is No or missing and up to including 30 days after the end of investigational product or the End of Study date, whichever is earlier.

Reflexive Approach for LDL-C and VLDL-C

For all analyses related to LDL-C and VLDL-C, unless specified otherwise, a reflexive approach will be used. When calculated LDL-C is less than 40 mg/dL or triglycerides are > 400 mg/dL, the ultracentrifugation LDL-C and VLDL-C value from the same blood sample will be used instead of calculated LDL-C and VLDL-C, if available.

6. Analysis Sets

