9.7.4 Analyses of Biomarker Endpoints

Not applicable.

10. Changes From Protocol-specified Analyses

There are no changes to the protocol-specified analyses.

11. Literature Citations / References

National Cholesterol Education Program (NCEP) Expert Panel on Detection, Evaluation, and Treatment of High Blood Cholesterol in Adults (Adult Treatment Panel III). Third Report of the National Cholesterol Education Program (NCEP) Expert Panel on Detection, Evaluation, and Treatment of High Blood Cholesterol in Adults (Adult Treatment Panel III) final report. *Circulation*. 2002;106:3143-3421.

12. Prioritization of Analyses

Not applicable.

13. Data Not Covered by This Plan

Currently there are no pre-planned analyses for the biochemical cardiovascular biomarker objective.

Protocol Number: 20170199

Date: 09 March 2019 Page 17 of 19

14. Appendices

Protocol Number: 20170199

Date: 09 March 2019 Page 18 of 19

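### SAP 9.6.8 drops the protocol's total-dose summary although SAP Section 10 declares no changes, and the exposure measure that remains ignores doses between the first and the last

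*SAP*

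**What the plan says.** Protocol 10.4.2.3.3 plans two exposure summaries: "The number of days on investigational product and the total dose of investigational product will be summarized using descriptive statistics". SAP 9.6.8 plans: "Descriptive statistics will be produced to describe the patient-month exposure to investigational product and patient-month duration of study participation". Total dose does not appear there, and no other SAP section tabulates total dose or number of administrations. SAP Section 10 nevertheless states: "There are no changes to the protocol-specified analyses".

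The exposure period is defined in SAP 5.3. Its upper end is "min (Last IP Dose Date + 28 days, EOS Date"), from which the first dose date is subtracted. One day is then added and the result is converted to months.

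The same SAP section defines the product as a monthly regimen only: "IP is Repatha 420 mg QM SC". SAP 3.1 says of subjects on apheresis that "they may receive Repatha 420 mg SC every 2 weeks to correspond with their apheresis schedule", and Protocol Table 7-1 gives the frequency as "420 mg QM (subjects on apheresis: 420 mg Q2W").

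**The concern.** The protocol and the SAP disagree on a planned analysis, and the SAP section meant to disclose such differences says there are none. A reader who relies on Section 10 would expect a total-dose table and not find one.

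The measure that remains does not replace it. An interval from first to last dose plus 28 days shows how long a subject was nominally covered, not how many doses were given in between. Intermediate doses can plausibly be missed in this design. The week 4 dose may be self-administered at home by any subject, and the week 2 and 6 doses by subjects on apheresis. Protocol 5.1 encourages follow-up to the end of the study whatever the adherence. Protocol 7.6 has non-compliance recorded in the eCRF, but the SAP plans no summary of doses received. In a post-marketing safety study whose primary objective concerns 12 weeks of exposure, the amount of drug received is basic context for the safety tables.

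**Working it through.** The documents state no exposure figure, so there is nothing to reproduce. The check applies the SAP 5.3 formula to dosing patterns that the protocol allows.

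**Inputs**
- Dose per administration: 420 mg (Protocol Table 7-1), with no dose adjustments (Protocol 7.4).
- Dosing weeks: 1, 4 and 8 for all subjects, plus 2 and 6 on the apheresis schedule (Protocol 5.3.2).
- Target days: week 8 = day 57, week 12 = day 85 (SAP Appendix A). Week 4 is taken as day 29 and week 6 as day 43, on the same spacing; this is my assumption.

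**Formula (SAP 5.3)**

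Months = [min(last dose + 28, EOS) − first dose + 1] / 365.25 × 12

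**Last dose on day 57, EOS on day 85**

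min(57 + 28, 85) = 85; 85 − 1 + 1 = 85; 85 / 365.25 × 12 = 2.79 months.

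**Last dose on day 29 (monthly schedule, week 8 missed)**

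min(29 + 28, 85) = 57; 57 / 365.25 × 12 = 1.87 months.

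**Last dose on day 43 (two-weekly schedule, week 8 missed)**

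min(43 + 28, 85) = 71; 71 / 365.25 × 12 = 2.33 months.

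| Pattern | Doses | Total dose | Exposure |
|---|---|---|---|
| Monthly, week 4 missed | 2 | 2 × 420 = 840 mg | 2.79 months |
| Monthly, complete | 3 | 3 × 420 = 1260 mg | 2.79 months |
| Two-weekly (apheresis), complete | 5 | 5 × 420 = 2100 mg | 2.79 months |
| Monthly, week 8 missed | 2 | 2 × 420 = 840 mg | 1.87 months |
| Two-weekly (apheresis), week 8 missed | 4 | 4 × 420 = 1680 mg | 2.33 months |

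Among subjects who all show 2.79 months, the dose ratio is 1260/840 = 1.5 on the monthly schedule alone. It is 2100/840 = 2.5 if two-weekly subjects are present.

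**Sensitivity to dates.** Moving the week 8 and week 12 visits within the ±7 days of Protocol 9.1.2 gives 78/365.25 × 12 = 2.56 to 92/365.25 × 12 = 3.02 months. The value still depends only on dates, not on the number of doses.

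**The case against.** The strongest reply is that this is one row missing from a descriptive table. No inference is planned, the patient-month summary covers the protocol's days on product in another unit, and some missed doses may surface as important protocol deviations. All of that is fair and it limits the severity. It does not make the statement in Section 10 correct, and a deviation listing is not a summary of dose.

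A reader might infer more than the documents support in four ways:

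- **That the 2.5-fold range applies generally.** The 2100 mg end exists only on the apheresis schedule. Neither document says how many such subjects are expected, and Protocol 3.2.1 notes that apheresis is not readily available in India. Without them the range is 1.5-fold.
- **That the formula hides every missed dose.** It does not. A missed week 8 dose shortens the exposure period; only doses between the first and the last go unseen.
- **That without total dose the adverse event incidence cannot be related to dose.** The protocol plans only an aggregate dose summary, and neither document plans adverse events by dose. Restoring the row would describe exposure but would not create that link.
- **That pooling apheresis subjects in the week-12 lipid summaries is part of the same fault.** Pooling follows the no-subgroup rule in Protocol 10.2.3 and SAP 4.2, so it is not a departure from the protocol.

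A practical objection also stands. It is not certain that home doses can be counted cleanly. For doses given outside the clinic, the only date form that SAP 5.1 names is the one for the final dose. Table 7-1 says "The amount dispensed, amount returned, date dispensed, date returned, package lot number of Repatha is to be recorded", but it does not say whether pens used in clinic are logged as dispensed or whether used pens count as returned. Simply adding dispensed minus returned to the in-clinic records could count the same pens twice.

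**Conclusion.** The point holds and is minor. The SAP omits an exposure summary that the protocol specifies and states that nothing has changed. The retained measure gives 2.79 months for 840 mg and for 1260 mg, and for 2100 mg if anyone is on the apheresis schedule. These equalities assume doses on days 1 and 57 and end of study on day 85; the 840 mg case also needs the week 4 dose to be the one missed.

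The primary endpoint, the subject incidence of treatment-emergent adverse events, is unaffected. The loss is confined to describing how much drug was received, for which total dose is the only measure the protocol plans.

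The product definition in SAP 5.3 conflicts with SAP 3.1 and Table 7-1. The exposure and treatment-emergence rules run on dates, so no planned figure depends on that definition, but the passages must be reconciled.

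**What to change.** 1. In SAP 9.6.8, restore the descriptive summary of total dose and add the number of doses received, derived from the recorded administrations. State how home doses are counted, with a rule that does not count pens used in clinic twice. If the sponsor prefers not to report total dose, declare the removal and the reason in SAP Section 10.
2. Reconcile the definition of investigational product in SAP 5.3 with SAP 3.1 and Protocol Table 7-1.

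The cost is one or two table rows, a short derivation rule and one definition line, or a single sentence in Section 10 if the removal is declared. In-clinic administrations and dispensed and returned amounts are already to be recorded. The one thing to confirm before database lock is whether the home administrations between first and last dose can be identified from those records.

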9.6.9 Exposure to Non-investigational Product

Not applicable.

9.6.10 Exposure to Other Protocol-required Therapy

Not applicable.

9.6.11 Exposure to Concomitant Medication

Throughout the study, investigators may prescribe any concomitant medications or treatments deemed necessary to provide adequate supportive care except for those listed in protocol Section 7.1.7. The number and proportion of subjects receiving concomitant therapies will be summarized by preferred term as coded by the World Health Organization Drug (WHO DRUG) dictionary.

Protocol Number: 20170199

Date: 09 March 2019 Page 16 of 19

